3.5. Preliminary data: effects of a single-dose of inorganic nitrate in HFpEF

We performed a randomized double-blind cross-over trial (clinicaltrials.gov NCT01919177) of a single dose of 12.9 mmol of inorganic nitrate given as 140 mL of concentrated nitrate-rich beetroot juice (NR-BR; Beet it; Sport, James White Drinks Ltd., Ipswich, UK) versus an otherwise identical beetroot juice which had been nitrate-depleted (used as the control or "placebo" juice, PB), allowing for a genuine double-blinded design.¹⁰² The intervention was given before a maximaleffort cardiopulmonary exercise test, with both experiments separated by a wash out period of at least 5 days (mean=11.8 days). We administered NR-BR 3 hours prior to testing because this period of time has been shown to correspond to peak circulating nitrite levels after oral nitrate administration. We tested the hypothesis that a single dose of inorganic nitrate would increase exercise capacity in HFpEF and assessed key physiologic adaptations to exercise. Specifically, we assessed: (1) Peak oxygen consumption (VO₂); (2) Total work performed; (3) Exercise efficiency, defined as the ratio of total work performed to total O_2 consumed (efficiency has been improved by inorganic nitrate in young athletes)^{70, 103-107}; (4) Exercise vasodilatory reserve (the change in peripheral vascular resistance from rest to peak exercise, normalized to the resting value); (5) Skeletal muscle mitochondrial oxidative function; (6) Aortic augmentation index, a metric of late systolic load.

We included subjects with symptomatic HF who had a preserved LV EF (>50%) and who were required to have a ratio of the early mitral inflow velocity (E) to septal tissue Doppler velocity (e') >8 and at least one other sign of chronically-elevated filling pressures including: (1) left atrial volume index >34 mL/m²; (2) elevated NT-pro-BNP level; or (3) elevated filling pressures (pulmonary capillary wedge pressure > 12 mmHg) on prior cardiac catheterization. Subjects had to be on stable medical therapy. Exclusion criteria included non-cardiac conditions limiting exercise tolerance (i.e. orthopedic issues, peripheral arterial disease with claudication, neuromuscular disorders); gait instability; rhythm other than sinus; infiltrative or hypertrophic cardiomyopathy; pericardial disease; primary pulmonary arteriopathy; coronary revascularization within 60 days; clinically significant valvular disease; clinically significant lung disease felt to contribute to exercise intolerance; significant ischemia seen on stress testing within the past year and not revascularized.

After each intervention, we performed a resting echocardiogram and arterial tonometry, followed by a maximal-effort supine-bicycle cardiopulmonary stress test using a graded exercise protocol, beginning at 15 Watts (W) for 3 minutes, increasing to 25 W for 3 minutes, then increasing by 25 W every 3 minutes thereafter.¹⁰⁸ Measurements during exercise included expired gas analyses (ParvoMedics True One 2400; Parvomedics, Utah, USA), echocardiographic assessments of stroke volume and continuous interrogation of muscle oxygenation of the left gastrocnemius

muscle with near-infrared spectroscopy (Portamon MkII device, Artinis medical systems; The Netherlands). We also assessed mitochondrial oxidative function measured via the recovery of oxygen consumption (measured with near-infrared spectroscopy) in forearm skeletal muscle after a bout of handgrip exercise, which corresponds to the phosphocreatine recovery kinetics, as previously described and validated against ³¹PMRI.^{109, 110} Details of the procedure may be found in previous publications. ^{108,109-111} In brief, the procedure measures the rate of oxyhemoglobin decline during brief high pressure inflations (at 200 mHg using a rapid inflation system), during which the decline in local muscle O₂ is due exclusively to consumption, as the arterial occlusion removes the confounding impact of arterial inflow. After a brief bout of forearm exercise, several of such brief occlusions are performed, allowing for assessments of the rate of O₂ consumption, which upon cessation of exercise, declines towards baseline in a mono-exponential fashion. This is characterized by a time constant (τ, tau) that corresponds to the time constant of PCr recovery kinetics.^{109, 110} Although we used this relatively inexpensive near-infrared spectroscopy procedure in our pilot trial, we will use more informative MRI techniques in this proposal.

[figure not shown]
Participants' mean age was 66±9 years. The population was enrolled from the Philadelphia VA Medical Center and was 88% male and 82% African-American (we will explicitly assure adequate representation of women in the KNO₃CK OUT HFpEF trial). Subjects were obese (BMI 35.4±5.4), had a high prevalence of hypertension (100%). Median NT-pro-BNP was 326 (IQR=290-352) pg/mL. Mean LA volume index was $35.7\pm10.9 \text{ mL/m}^2$. Serum NO metabolites were markedly greater after NO₃⁻ supplementation (median 326.0 [IQR 290.0-352.0] versus 10.0 [IQR 9.0-13.0] μ M, *P*=0.0003).

[figure not shown]
3.5.1. Changes in exercise capacity and oxygen uptake: Nitrate supplementation resulted in a greater peak VO₂ (12.6±3.7 versus 11.6±3.1 mL O₂/kg/min; *P*=0.005) and total work performed (55.6±35.3 vs. 49.2±28.9 kJ; *P*=0.04). Ventilatory threshold (a marker of the cellular anaerobic threshold) was greater following NO₃- supplementation (7.6±1.8 versus 7.0±1.4 mL O₂/kg/min, P=0.03). Because total work performed and O₂ consumption increased in tandem, exercise efficiency was no different. This is interestingly, different than the effect seen in athletes and younger subjects, among whom exercise efficiency increases^{70, 103-107}, demonstrating the importance of characterizing specific adaptations to exercise in this particular patient population.

3.5.2. Exercise vasodilatory reserve: NR-BRJ led to a significant fall in systemic vascular resistance (SVR) at peak exercise (-42±17%) compared to PB (-32±20%; P=0.03). This was accompanied by an increase in cardiac output (% change in NR-BRJ 122±60 vs PB: 89±53%, P=0.006), increased heart rate (78.0±24.1 versus 65.6±21.0%, P=0.001) and a trend towards greater stroke volume (22.6±22.4 versus 12.7±25.4%, P=0.13).

3.5.3. Effects on filling parameters: Interestingly, we found no evidence of reduced preload, since end-diastolic volume (EDV) significantly increased with beetroot supplementation (112±12 mL vs 93±6 mL; P=0.04), whereas the E/E' ratio did not change (NR-BRJ: 12.1±0.9 vs. PB: 11.5±0.8; P=0.90). The increased LV EDV may suggest improvements in diastolic function, which we plan to further assess in this proposal using measurements of intraventricular pressure gradients.

**3.5.4.** Augmentation index: The aortic Alx (derived from radial tonometry) was significantly decreased by NO₃- supplementation (NO₃- 132.2 \pm 16.7 versus PB 141.4 \pm 21.9%, P=0.03).

(mean arterial pressure change=0.17 mmHg; systolic BP change=0.7 mmHg; both P>0.85) with NO₃⁻ supplementation. This is in contrast to BP-lowering effect in healthy volunteers and drug naïve hypertensive subjects^{112, 113} and likely explained by recent data indicating that the BPlowering effect of inorganic nitrate is mediated by its renal effects in pathways downstream of the AT1-receptor.¹¹⁴ These effects are likely attenuated in patients who are treated with ACE inhibitors/angiotensin receptor blockers for BP control (such as occurs in HFpEF patients).

In summary, a single dose of inorganic nitrate increased peak VO₂ and total work during a symptom-limited maximal effort exercise test. It enhanced the exercise vasodilatory reserve, without affecting SVR or blood pressure at rest. It also reduced late systolic LV load, which is implicated in diastolic dysfunction and LV remodeling. Nitrate also led to increased cardiac output during exercise, likely from a reduced afterload, but potentially also mediated by increased EDV (suggesting effects on diastolic function). Finally, in accordance with other studies, our pilot data suggest an improvement in mitochondrial oxidative function, suggesting improved ATP production.^{115, 116} However, nitrate did not affect the O₂ cost of exercise, as has been demonstrated in younger and/or healthier populations.^{70, 105, 106, 117, 118} This demonstrates the importance of having disease-specific and agent-specific data to design our phase IIb trial. Our pilot trial was limited by its small sample size, inclusion of mostly men (we will explicitly assure

adequate representation of women in this trial). However, it does support the need for a larger phase IIb randomized trial of prolonged nitrate supplementation in HFpEFp.

3.6 Effect on Myocardial Perfusion Reserve in HFpEF ("Cardiac MRI sub-study")

Myocardial biopsy studies in HFpEF patients have revealed cardiomyocyte hypertrophy, interstitial myocardial fibrosis, incomplete myocardial strip relaxation, increased cardiomyocyte stiffness, increased production of reactive oxygen species at the coronary endothelial cell level, along with increased expression of adhesion molecules and production of pro-inflammatory cytokines.¹¹⁹⁻¹²² In view of these findings, a new paradigm has been suggested in the pathophysiology of HFpEF (Figure 3). The paradigm proposes that the co-morbidities seen in HFpEF patients induce a proinflammatory state which activates coronary microvascular endothelial cells to produce reactive oxygen species and induces cardiomyocyte hypertrophy resulting in concentric LV remodeling and increased interstitial collagen deposition proceeding to diastolic dysfunction.

[figure not shown]

Figure 3: Adapted from Paulus et al. Novel paradigm in HFpEF patients. JACC Volume 62, Issue4 (236-271)

MRI is an ideal tool to assess these pathophysiological phenotypes and assess the effect of KNO₃ on microvascular myocardial function. Coronary microvascular dysfunction which is proposed to underlay this disease process can be estimated by measuring MPR by means of quantitative vasodilator stress cardiac MRI. MPR is calculated by a ratio of stress coronary perfusion over rest perfusion. Myocardial fibrosis can be quantitatively assessed by the measurement of ECV by myocardial T1 mapping.¹²³

The ancillary study of the KNO₃CK OUT HFpEF trial represents a unique opportunity to assess the effect of inorganic nitrates on MPR values in this patient population.

4. STUDY DESIGN AND POPULATION

4.1. Overview of study design

In this phase IIb, double-blind, cross-over placebo-controlled trial, we will assign 84 subjects with HFpEF to: (A) Potassium nitrate administered by mouth at a dose of 6 mEq three times daily for approximately 6 weeks, or (B) Potassium chloride (KCI) at identical doses. The order of the interventions (AB-BA design) will be randomized, with a 1-week washout period separating each

intervention. A crossover design will enable each subject to receive both treatments, reducing inter-individual variability and maximizing our power to detect effects of potassium nitrate vs. placebo (KCl). The active drug (KNO₃-) and control (KCl) will be prepared at the Investigational Drug Pharmacy at the University of Pennsylvania and dispensed by an investigational drug pharmacist, blinded to both the subjects and the investigators.

4.2 Study Sites

The three sites for this trial will be the Hospital of the University of Pennsylvania, Northwestern University and the Corporal Michael J. Crescenz VA Medical Center.

4.3. Study Population

We will enroll 84 subjects meeting the following criteria. Eligibility will be determined by the site PI according to the criteria outlined below.

4.3.1. Inclusion Criteria:

- 1. Adults aged 18-90 years of age
- 2. A diagnosis of heart failure with NYHA Class II-III symptoms
- 3. LV ejection fraction >50% during baseline echocardiography
- 4. Stable medical therapy: no addition/removal/changes in antihypertensive medications, or betablockers in the preceding 30 days
- 5. Elevated filling pressures as evidenced by at least 1 of the following:
 - a. Mitral E/e' ratio > 8 (either lateral or septal), with low e' velocity (septal e'<7 cm/sec or lateral e'< 10 cm/sec), in addition to one of the following:
 - i Enlarged left atrium (LA volume index >34 ml/m²)
 - ii Chronic loop diuretic use for control of symptoms
 - iii Elevated natriuretic peptides (BNP levels >100 ng/L or NT-proBNP levels >300 ng/L)
 - b. Mitral E/e' ratio > 14 (either lateral or septal)
 - c. Elevated invasively-determined filling pressures previously (resting LVEDP>16 mmHg or mean pulmonary capillary wedge pressure [PCWP] > 12 mmHg; or PCWP/LVEDP≥25 mmHg with exercise)
 - d. Acute heart failure decompensation requiring IV diuretics

4.3.2. Exclusion Criteria:

- 1. Supine systolic blood pressure <100 mm Hg
- 2. Pregnancy: Women of childbearing potential will undergo a pregnancy test during the screening visit
- 3. Orthostatic hypotension defined as >20 mm Hg decrease in systolic blood pressure 3-5 minutes following the transition from the supine to standing position
- 4. Uncontrolled atrial fibrillation, as defined by a resting heart rate>100 beats per minute
- 5. Hemoglobin < 10 g/dL
- 6. Inability/unwillingness to exercise
- 7. Moderate or greater left sided valvular disease (mitral regurgitation, aortic stenosis, aortic regurgitation), any degree of mitral stenosis, severe right-sided valvular disease, or presence of a prosthetic valve in the mitral position

- 8. Hypertrophic, infiltrative, or inflammatory cardiomyopathy
- 9. Clinically significant pericardial disease, as per investigator judgement.
- 10. Current angina
- 11. Acute coronary syndrome or coronary intervention within the past 2 months
- 12. Primary pulmonary arteriopathy
- 13. Clinically significant lung disease as defined by: Chronic Obstructive Pulmonary Disease meeting Stage III or greater GOLD criteria, treatment with oral steroids within the past 6 months for an exacerbation of obstructive lung disease, or the use of daytime supplemental oxygen
- 14. Ischemia on stress testing without either (1) subsequent revascularization, or; (2) a subsequent angiogram demonstrating the absence of clinically significant epicardial coronary artery disease, as per investigator judgement.
- 15. Left ventricular ejection fraction <45% in any prior echocardiogram or cardiac MRI, unless this was in the setting of uncontrolled atrial fibrillation.
- 16. Treatment with phosphodiesterase inhibitors that cannot be withheld
- 17. Treatment with organic nitrates
- 18. Significant liver disease impacting synthetic function or volume control (ALT/AST > 3x ULN, Albumin <3.0 g/dL)
- 19. eGFR < 30 mL/min/1.73m²
- 20. G6PD deficiency. In males of African, Asian or Mediterranean decent, this will be formally evaluated by enzyme testing prior to drug administration. A negative screening test for G6PD will be required in these subjects for inclusion in the study. If a quantitative test is being performed, a clinically significant reduction in G6PD activity (<60% of normal) will exclude subjects.
- 21. Methemoglobinemia baseline methemoglobin level >5%
- 22. Serum K>5.0 mEq/L
- 23. Severe right ventricular dysfunction
- 24. Any medical condition that, in the opinion of the investigator, will interfere with the safe completion of the study.
- 25. Contraindications to MRI (except as noted below), including the presence of a pacemaker, metal implants, claustrophobia, or that have known medical conditions which can be exacerbated by stress such as anxiety or panic attacks. Inability to lie flat in the MRI scanner for 90 minutes is also an exclusion criterion.

Participants who have contraindications for MRI but are otherwise good candidates for the study, may be enrolled. In this case, participants will undergo all study procedures except for the MRI scans.** (See paragraph below for more detail)

In addition, specific exclusion criteria for undergoing scanning in the 7-Telsa MRI scanning system include (these will only apply when the 7T scanner is used. In addition, a 3T scanner is also available at Penn, allowing the choice of the scanner depending on availability (to maximize safety, exclusion criteria for 7T will be applied at Penn for all participants, even if they ultimately are scanned at 3T):**

- ANY intra-luminal implant, filter, stent, or valve replacement
- ANY type of life assist device, pump, or prosthetic
- ANY vascular clip or clamp

- ANY surgically placed clips or clamps or bands on visceral organs
- ANY intracranial implants of any type other than dental fillings
- ANY non-removable piercings, jewelry, or medicinal patch
- ANY personal history of intraocular injury or fragment in or around the orbit that cannot be cleared through radiologic examination
- ANY personal history of bullet, shrapnel, or stabbing wounds that cannot be cleared through radiologic evaluation.

** If any of the above apply, we may investigate the issue further to ensure subject safety. This may include obtaining X-rays or obtaining reports from prior radiographic studies. We may also discuss the case with our radiologists and MRI technicians. In these circumstances, an MRI will only be performed if deemed safe by an attending radiologist on a case-by-case basis.

Subjects that qualify for a 3T or 7T scanner (for the leg MRI study) also qualify for scanning in a 1.5T scanner (for the cardiac MRI substudy). However, the opposite is not necessarily true. Subjects who are determined eligible to undergo scanning in a 3T or 7T scanner (in the primary study) are eligible to undergo scanning in the 1.5T scanner (for the cardiac MRI study). Some situations (such as many intraluminal stents and prosthetic valves) which would exclude scanning at high field (7T or 3T) are considered safe for 1.5T scanning. Subjects who are deemed ineligible to undergo 7T or 3T scanning in the parent trial, may still be enrolled in the ancillary myocardial perfusion study and undergo a cardiac MRI study (at 1.5T). In all cases, participation in the myocardial perfusion / cardiac MRI ancillary study will be approved by [name], who has appropriate clinical expertise to assess the safety of this test, according to current clinical standards. [name] is the Director of Advanced Cardiac Imaging at the CMJC Philadelphia VA Medical Center and Assistant Professor at the University of Pennsylvania.

4.3.3. Criteria that will prompt exclusion from the trial at the 6 week visit

Subjects will be discontinued from study participation if they meet any of the following criteria at the 6-week study visit:

- 1. Acute coronary syndrome or coronary intervention for unstable coronary disease after enrollment
- New onset ischemia on stress testing since the time of enrollment, including clinically significant reversible ischemia in a coronary distribution identified during the cardiac MRI substudy.
- 3. New treatment with organic nitrates or phosphodiesterase inhibitors that cannot be withheld
- 4. Serum K>5.5 mEq/L
- 5. Any medical condition that, in the opinion of the investigator, will interfere with the safe completion of the study, or the validity of endpoint assessments. Although the ultimate authority/decision making will rely on each site PI, these ad-hoc discontinuations will be discussed with the other site PIs, the chair of the trial and the medical director of the IND for input.

Subjects who meet the criteria below will not be immediately discontinued, but will be scheduled for an ad hoc additional visit for reassessment of values prior to drug initiation in phase 2:

- 1. Supine systolic blood pressure <90 mm Hg
- 2. Acute kidney injury with eGFR < 30 mL/min/1.73m2
- 3. Methemoglobinemia baseline methemoglobin level >5%

If these criteria persist during the ad-hoc visit, the subject will be discontinued from the study.

4.3.4 Conditions that will preclude participation in the myocardial perfusion ancillary study include:

- 1. Prior allergic reactions to gadolinium-based contrast agents.
- 2. Allergy, or prior severe adverse reactions to regadenoson or aminophylline.
- 3. 2nd degree AV block, 3rd degree AV block or high-grade AV block.

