At approximately 5 weeks into each interventional phase, the Aurora and Actigraph devices will be given to the subjects. The goal will be for the subjects to wear these devices during the final week of each interventional phase to look for differences with each therapy. The devices will be brought back by the subject at his/her next visit.

6-week endpoint assessment: Following ~6-weeks of therapy with KNO₃/KCl, subjects will return for a repeat endpoint assessment. Physical examination with measurement of orthostatic blood pressure, pill count, KCCQ, dietary counseling, cognitive assessment, and side effect assessments will be performed. A urine pregnancy test will be performed in women with childbearing potential. An intravenous catheter will be placed in the antecubital vein and securely fixed in place. Blood, urine, and saliva samples will be collected prior to, and approximately 2 hours after, morning dose administration, given with a standardized low-nitrate breakfast. Blood RNA samples will be collected prior to the morning dose administration using Paxgene tubes (BD Biosciences, Franklin Lakes, NJ). Subjects will then undergo repeat echocardiography, arterial tonometry, and blood pressure measurements (including BP+ central blood pressure measurements). Subjects will then perform a maximal-effort peak oxygen consumption (VO₂) test using a supine bicycle exercise test with expired gas analysis. Cardiac output at rest will be measured immediately prior to exercise using pulsed wave Doppler echocardiography. Exercise cardiac outputs will also be obtained using the same technique. An additional blood sample will be obtained at peak exercise. The Aurora watch will be worn during exercise when possible. Subjects enrolled at Penn or the VA will undergo repeat assessment of skeletal muscle mitochondrial oxidative capacity using MRI either before, or at least 3 hours after, peak VO_2 testing. Based on scheduling and availability, the MRI may be performed on a different day than the exercise study. The Kansas City Cardiomyopathy Questionnaire (KCCQ) will be administered. Following the final endpoint assessment, subjects' participation in the study will be over.

Phase 2: 6-Week Visit (final visit) Procedures

- Interim medical history, concomitant medications
- Physical exam (including orthostatic vital signs)
- Pill count and side effect assessment
- Blood, urine, and sputum measurements, followed by blinded drug administration

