8. STUDY MEASUREMENTS AND DATA COLLECTION

8.1. Assessment of exercise capacity

We will use a supine bicycle exercise protocol in conjunction with expired gas analysis to assess oxygen consumption (VO₂) during exercise. Subjects will perform a maximal exertion limited exercise test using a graded-exercise protocol. We will use a supine cycle ergometer designed for stress echocardiography (Stress Echo Ergometer 1505, Medical Positioning, Inc, Kansas City, MO). Subjects will undergo expired gas analysis with a Parvo Medics True One 2400 device (Parvo Medics, Sandy, UT), an Innocor device (Innovision Inc) or equivalent. Resistance began at 15 W for 3 minutes, increasing to 25 W for 3 minutes, and then increasing by 25 W every 3 minutes thereafter. Breath-by-breath information will be recorded. We will use custom-designed software already developed in Matlab (MathWorks, Natick, MA) at our lab for offline processing and quantification of all exercise data.¹¹¹ All data quantification will be blinded to treatment. Total work performed will be computed and exercise efficiency will be defined as (total work/total oxygen consumed). Exercise efficiency is not a formal endpoint of the trial, but will be used to interpret changes in the co-primary outcomes.

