8.4. Assessment of muscle perfusion and energetics

If available equipment and personnel are available at the time of enrollment, MRI studies will be performed at rest and immediately after a standardized plantar flexion exercise test using a 3T or a 7T scanner equipped with a 15-channel transmit/receive radiofrequency coil and an MR compatible pneumatically controlled foot pedal. Phase contrast MRI using a fast 1D projection technique¹²⁵ will be used to image blood flow with high temporal resolution (Figure 5a-c).

The primary measure of recovery kinetics will be measured with creatine chemical exchange saturation transfer (CrCEST), except for subjects enrolled at the Northwestern site. Sample CrCEST recovery images of the calf are shown in figure 5d. The first 2 acquisitions are preexercise (red box), with the remainder representing sequential acquisition immediately after cessation of exercise. Recovery kinetics of creatine levels will be quantified. Phosphorus spectroscopy is limited by the lack of anatomic information, being able only to assess PCr levels in a large voxel of tissue. In contrast, the chemical exchange saturation transfer (CEST) technique, a novel sensitivity enhancement method developed by our group,^{75, 126-128} can detect metabolite content based on exchangerelated properties at either 7T^{127, 128} or 3T,¹²⁶ utilizing hydrogen signal (thus not depending on the much weaker phosphorus signal). Creatinine exhibits a concentration dependent CEST effect between its amine (-NH₂) and bulk water protons (CrCEST)⁷⁵ which allows for the monitoring of Cr concentration changes with high spatial and temporal resolution. In contrast to phosphorus spectroscopy, this technique allows for spatial mapping (creation of an highresolution anatomic image) of PCr levels (figure 3D). This cannot be accomplished with phosphorus spectroscopy. This novel technique can be used to assess PCr recovery kinetics following exercise, allowing for accurate selection of muscle tissue (rather than fat or bone). More importantly, the serial anatomically mapped PCr information can be used to assess muscle fat using a 3-point Dixon separation technique and hydrogen spectroscopy. We will exclude fat from CrCEST computations.

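### Leg MRI at Penn may be done at 3T or 7T by availability, and nothing keeps a subject's two crossover scans at the same field strength

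*Combined protocol and SAP*

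**What the plan says.** Section 4.1 gives the reason for the design: "A crossover design will enable each subject to receive both treatments, reducing inter-individual variability and maximizing our power". Section 10.2 first tests paired within-subject differences. It then fits a mixed model with period, sequence and a random subject effect. No equipment term is named.

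On the leg scanner, section 4.3.2 says that "a 3T scanner is also available at Penn, allowing the choice of the scanner depending on availability". It applies the 7T safety exclusions to every Penn participant, including those who are in the end scanned at 3T. Section 8.4 has the scans performed "immediately after a standardized plantar flexion exercise test using a 3T or a 7T scanner". Sections 5.3 and 5.5 place a leg MRI at the end of each phase for Penn and VA subjects, and both add: "Based on scheduling and availability, the MRI may be performed on a different day than the exercise study". Northwestern does no leg MRI.

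On the gas analyser, section 8.1 says: "Subjects will undergo expired gas analysis with a Parvo Medics True One 2400 device (Parvo Medics, Sandy, UT), an Innocor device (Innovision Inc) or equivalent". The pilot that supplied the standard deviation for peak VO2 names one model in section 3.5: "expired gas analyses (ParvoMedics True One 2400; Parvomedics, Utah, USA".

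The documents contain no rule that a subject's two phases use the same scanner, field strength, coil or analyser. They do not ask for the device to be recorded and describe no cross-calibration.

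**The concern.** A crossover removes whatever is constant within a subject. A scanner effect is constant only if the scanner is. If a Penn subject is scanned at 7T in one phase and 3T in the other, the difference between field strengths enters that subject's treatment contrast. Stratifying randomisation by site does not remove it, nor does a random subject effect, because the change happens inside the subject. The period term removes only a shift that affects both sequences alike.

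The endpoints exposed are muscle blood flow and the Cr recovery time constant (secondary) and the spatial matching of flow and oxidative capacity (exploratory). The same argument would apply to peak VO2, a co-primary endpoint, if the analyser could change between a subject's two tests.

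**Working it through.** **What the text permits.** Section 4.3.2 makes availability the basis for choosing the scanner at Penn. Section 8.4 restricts leg MRI to cases where equipment and staff are available at enrolment; that governs whether MRI is done, not which field strength is used. The scans come at the end of each phase, about 7 weeks apart (1 week of washout plus about 6 weeks of treatment). A switch is therefore permitted. The documents do not show that any switch took place.

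**Formula.** Let b be the shift caused by a device change and f the share of subjects who switch. If switching is independent of treatment, so that shifts favour either treatment equally often, the variance of the paired difference becomes SD² + f × b². The documents give neither b nor f, so every value of b and f below is an assumption.

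**The plan's own power figure.** Section 10.1 gives a difference of 0.6 ml/kg/min, an SD of change of 1.23, 84 enrolled, 90% retention, two-sided alpha of 0.05 and 80% power.
- Pairs: 84 × 0.9 = 75.6, taken as 75.
- Standardised effect: 0.6 / 1.23 = 0.488, which matches the stated 0.49.
- Paired t-test power at 75 pairs: 98.6%. The stated 80% is not reproduced, and the gap is on the conservative side. That is a separate matter.

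**Peak VO2, if analysers did switch within subject.** Take b = 0.6 to 1.2 ml/kg/min (5-10% of a peak near 12) and f = 10-30%.
- Mildest case: 1.23² + 0.1 × 0.6² = 1.5129 + 0.036 = 1.549; SD 1.24; variance up 2%.
- Worst case: 1.5129 + 0.3 × 1.2² = 1.5129 + 0.432 = 1.945; SD 1.39; variance up 29%.
- Power for 0.6 ml/kg/min at 75 pairs with SD 1.39: about 96%.

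**Cr recovery.** Section 10.1 claims 80% power for a 5 s change and gives no SD. At 75 pairs, 80% power needs a standardised effect of 0.328, so the implied SD is 5 / 0.328 = 15.3 s.
- b = 5 s, f = 25% and 50%: SD 15.5 and 15.7; power 79% and 78%.
- b = 10 s, f = 25% and 50%: SD 16.1 and 16.8; power 76% and 72%.

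The MRI subset will be smaller than 75, because one site does no leg MRI, MRI-ineligible subjects may enrol and scans are done if feasible. Its size is not stated. As an illustration only, take 90% of the 46 Penn subjects in Appendix 2, about 41 pairs. With the same SD, power is 54% before any switching. It falls to 51-52% with a 5 s shift and to 46-49% with a 10 s shift. Most of the fall from 80% comes from having fewer pairs.

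**Which offsets reach the time constant.** If the recovery signal is S(t) = c + A·exp(−t/τ), then m + k·S(t) has the same τ. A constant signal offset or scaling between field strengths therefore does not by itself change the time constant. Only a difference that alters the shape of the fitted curve would. No such protection applies to muscle blood flow, where a shift enters the difference directly.

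**The case against.** The strongest reply is that the documents nowhere say equipment is chosen afresh at each visit. The scanner sentence sits in a safety-eligibility paragraph and could describe one choice per participant. For exercise equipment, section 8.3 describes variation by site, and section 8.1 may simply list what three sites own. A difference between sites cancels within subject. This stands in large part for the analyser. For the scanner it is weaker: availability is the stated basis, the scan is repeated, and nothing carries the first choice over to the second phase.

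A reader might infer that the co-primary result is at risk. The documents do not support that. The analyser choice is not described as made per test, the offsets are assumed, and power on the protocol's own inputs stays near 96% at the unfavourable end of the range. Total work, the other co-primary endpoint, comes from ergometer load and does not depend on the analyser.

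A reader might also infer a biased treatment effect. Sequence is randomised and treatment is blinded, so switching driven by availability should not depend on treatment. Uneven switching would then be chance imbalance, which is random error.

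Finally, Appendix 2 lists a manual of procedures that is not among the documents, and section 9.6.3 gives scan implementation and quality control to an MRI core laboratory. Either might already impose a same-scanner rule. That is possible, but the protocol neither states nor points to one.

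**Conclusion.** The point holds as a cheap improvement. The plan allows the leg MRI at Penn to be done at either field strength by availability, and it does not fix, record or model the field strength within subject. The expected harm is lost precision on secondary and exploratory MRI endpoints.

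The size cannot be determined from the documents. Over the ranges assumed here, the loss for Cr recovery is about 1 to 8 percentage points of power, and it could be nil if the scanners differ only by a constant offset or scaling of the signal. The calculation assumes that switching is independent of treatment and that the SD implied by the plan's power statement is right.

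The peak VO2 conclusion is not threatened. Matching the analyser is worth adding only because it costs almost nothing.

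**What to change.** - In section 8.4, state that each subject's two leg MRI scans use the same scanner field strength and the same coil.
- In section 8.1, state that both of a subject's exercise tests use the same gas analyser model.
- Add a field to the case report form that records the device used at each visit.
- In section 10.2, state that if a switch cannot be avoided, the pair is flagged and the affected endpoint's analysis is repeated without flagged pairs as a sensitivity analysis.

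The cost is one form field, a few sentences of text, and an occasional scan moved when the matching scanner is booked. Section 6 already provides for a window of one week either side of the 6-week visit. If equipment never changes within a subject in practice, the rule costs nothing beyond the form field.
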